Until now, several studies have stated that ultrasound examination can predict gastric volume. This examination is useful for assessing the patient who in an emergency condition with an unclear fasting condition that requires medical treatment soon. A study assessing gastric contents in fasting patients using ultrasound has not been done in Indonesia. Ultrasound of gastric contents has become an option in many countries such as Sweden, and Canada to assess the risk of perioperative aspiration.

Research Problems

Prolonged fasting can negatively affect the patient, especially the patient with a high risk of anesthesia. Currently, in RSCM, 6 hours of fasting is considered sufficient as preparation for elective surgery. There are differences from the ASA guidelines that state recommendations for 6-hours fasting after snacks and 8-hours fasting after solid foods. This research aims to analyze the difference in gastric volume after 6-hours of fasting compared with 8-hour fasting in patients undergoing elective surgery.

Research purposes

This study aims to compare gastric volume in fasting patients as preparation for elective surgery. Prolonged fasting has a negative impact on the patient's condition, especially patients with risk factors such as sepsis, diabetes, and various other conditions. If there is no significant difference in gastric volume after 8 hours of fasting compared to gastric volume after 6 h of fasting, then a 6-hour fasting period may be considered to reduce the risk of aspiration in the patient who will undergo elective surgery.

Research Methods

Research design

This is a cohort study of patients undergoing non-digestive elective surgery. This research was conducted in the hospital ward RSUPN dr. Cipto Mangunkusumo from January to February 2019. The estimated number of samples with an estimated *drop out* of 10% are 35 subjects. Sampling is done after obtaining approval from the Ethics Committee of the Faculty of Medicine, University of Indonesia.

Inclusion and Exclusion Criteria

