After the subjects agree to take part in the research, an initial examination will be carried out for obtaining subject demographic data, including age, weight and height, type surgery to be performed, and preoperative examinations. The subject will start 8 hours of fasting before the surgical planning time. Before fasting, the subjects were given standard food RSCM with standardized nutritional levels. Subjects were given 1 hour to consume the standard RSCM food. 6 hours after the standard meal is consumed, an ultrasound examination will be performed with the right lateral decubitus position to obtain ultrasound imaging of the antrum after 6 hours of fasting. After that, the subject continues fasting for up to 8 hours after consumption of solid food. Furthermore, an Ultrasound examination is performed using the same technique to obtain images of ultrasound imaging of the antrum after 8 hours of fasting. Imaging pictures are taken at the time relaxation of the antrum, between two contractions. The results of this imaging are stored and assessments of antrum craniocaudal (CC) and anteroposterior (AP) diameters were performed by research assistants who don't know when the image was taken. The volume of the stomach was calculated with the formula $GV = 27.0 + 14.6 \times CSA - 1.28 \times age$.

Statistical analysis

The data collected is processed using the Statistical Package for Social Scientist program (SPSS) version 23.0. Numerical data with normal distribution will be analyzed using the T-test

in pairs. If the data has an abnormal distribution, the data will be analyzed using the Wilcoxon test. The data obtained is the result of repeated examinations, so that the

analysis will be adjusted using the Bonferroni correction factor. Categorical data will be analyzed using the McNemar test. The results of data processing are displayed in tabular form. The CSA can be calculated with the formula $CSA = \frac{\pi \times CC \times AP}{4}$. The gaster volume was grouped into sufficient and insufficient with a border value of 1.5ml/kg.

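### The Bonferroni correction is justified by repeated measurement, which the paired tests already handle, and has no stated divisor, family of tests or alpha

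*Combined protocol and SAP*

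**What the plan says.** The Statistical analysis section of the combined protocol and SAP sets out three tests. For normally distributed measurements, "Numerical data with normal distribution will be analyzed using the T-test", and the next line specifies that the test is paired. Otherwise, "If the data has an abnormal distribution, the data will be analyzed using the Wilcoxon test". For categories, "Categorical data will be analyzed using the McNemar test". The category in view is gastric volume: "The gaster volume was grouped into sufficient and insufficient with a border value of 1.5ml/kg".

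Between the Wilcoxon and McNemar sentences comes the multiplicity rule: "The data obtained is the result of repeated examinations, so that the" "analysis will be adjusted using the Bonferroni correction factor". No alpha, divisor, list of tests covered or designated primary outcome appears anywhere in the document.

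Two other places bear on the point. The Data collection section describes one ultrasound at 6 hours and one at 8 hours in the same patient, by the same technique. The Research purposes section sets the decision rule: "If there is no significant difference in gastric volume after 8 hours of fasting compared to gastric volume after 6 h of fasting", a 6-hour fast may be considered.

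**The concern.** The rule gives a reason that belongs to a different problem. Measuring a patient twice makes the two values dependent, and a paired analysis deals with that. Bonferroni limits the chance of a false positive across several tests. Citing repeated examinations as the ground for it suggests that the two problems have been confused.

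The rule is also incomplete. Without an alpha, a family and a divisor, two analysts could apply different thresholds and both claim to have followed the plan, and the divisor could be settled after the data are seen. Because McNemar is introduced after the sentence, it is not clear whether the correction covers it.

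The direction of the effect matters here. In a trial that sets out to show a difference, an unneeded correction costs power but errs on the cautious side. Here non-significance is the outcome that favours the shorter fast, so a smaller alpha makes the favourable conclusion easier to reach. Type I error stays controlled; the risk that grows is that of missing a real difference.

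**Working it through.** **Number of contrasts.** With two time points there are 2 × (2 − 1) / 2 = 1 pairwise comparison per outcome. Bonferroni over time comparisons therefore has divisor 1 and changes nothing. A larger divisor needs either a count of examinations instead of comparisons, or a family of several outcomes. The plan states neither.

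**Sample size.** The Research design section says that the number of subjects with estimated dropout "of 10% are 35 subjects". The 35 cannot be derived in full, because alpha, power, effect size and SD are not given. Only the dropout step can be checked: 31 / (1 − 0.10) = 34.4, which rounds up to 35. About 31 evaluable pairs is therefore used below, with 35 as the case of no dropout.

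**Assumed inputs (none is in the plan).** Two-sided test, base alpha 0.05, divisor k from 1 to 3, and true mean paired difference d of 0.4 or 0.5 SD of the paired differences.

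**Observed difference needed for significance**, t_crit / √n with n = 31 and √31 = 5.568:
- k = 1 (alpha 0.05): 2.042 / 5.568 = 0.367 SD
- k = 2 (alpha 0.025): 2.360 / 5.568 = 0.424 SD
- k = 3 (alpha 0.0167): 2.536 / 5.568 = 0.455 SD

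An observed difference between 0.367 and 0.424 SD would be reported as significant with k = 1 and as non-significant with k = 2.

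**Chance of a non-significant result when a difference exists.** This is F(t_crit) − F(−t_crit), where F is the non-central t distribution with n − 1 degrees of freedom and non-centrality d√n. For n = 31 the non-centrality is 2.227 at d = 0.4 and 2.784 at d = 0.5.

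| Pairs | Divisor | d = 0.4 | d = 0.5 |
|---|---|---|---|
| 31 | 1 | 42% | 23% |
| 31 | 2 | 54% | 34% |
| 31 | 3 | 61% | 40% |
| 35 | 1 | 37% | 18% |
| 35 | 2 | 49% | 27% |

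From unrounded values, going from divisor 1 to 2 adds 0.5428 − 0.4225 = 12.0 points and 0.3353 − 0.2315 = 10.4 points with 31 pairs, and 0.4850 − 0.3672 = 11.8 points and 0.2721 − 0.1805 = 9.2 points with 35. A simulation of 200,000 trials with 31 pairs agrees: 0.419 to 0.541 at d = 0.4, and 0.230 to 0.333 at d = 0.5.

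**The case against.** The strongest reply is that the natural divisor is 1. There is one time contrast, and the title, aim and decision rule all point to gastric volume as the main outcome, so no result would change. This is correct on that reading, but it leaves a sentence that does nothing. The plan does not say that the divisor is 1, and a reader cannot rely on it.

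A second reply is that volume and the 1.5 ml/kg category are both tested, so a family of two is defensible and Bonferroni is a legitimate, conservative choice for it. This also stands as a possibility. On that reading the correction would be sound and only the stated reason wrong. But the plan does not define that family. Testing cross-sectional area (CSA) would not enlarge it: for a patient of fixed age, the volume formula makes the change in volume 14.6 times the change in CSA, so the paired t-test would be the same test.

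The wording might also mean repeated testing instead of repeated measurement. That is a less natural reading of a sentence about examinations, and it would still leave the divisor open.

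Two further points are fair. The magnitude rests wholly on assumed inputs. And the larger defect is that non-significance, with no margin, is taken as support for 6 hours. That defect exists whatever the divisor.

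Last, the document is dated June 2019 and gives January to February 2019 as the study period, so data may already have been collected. Dropping a stated correction at that stage needs open reporting. It does not make the rule valid.

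**Conclusion.** The concern holds. The stated reason for the correction is wrong, and its size is undefined; both follow from the text without any assumption. The consequence is conditional. With divisor 1 there is none. With divisor 2, a two-sided base alpha of 0.05, 31 to 35 pairs and a true difference of 0.4 to 0.5 SD, the chance of a non-significant result rises by about 9 to 12 percentage points. The direction does not depend on those inputs: any divisor above 1 favours the non-significant conclusion. The 18% to 42% chance of non-significance that remains at divisor 1 is due to sample size and is not caused by this rule. The plan should be changed here, although the point is less serious than the missing margin.

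**What to change.** Delete the Bonferroni sentence. In its place, state that the paired tests account for the repeated measurement, and that the 6-hour versus 8-hour difference in gastric volume is the single primary test at two-sided 0.05, reported with a 95% confidence interval. Label the McNemar comparison at 1.5 ml/kg as secondary.

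The cost is one sentence removed and two added, with no new data. The secondary comparison then has no multiplicity protection and should be read accordingly. If the team wants volume and category as co-primary outcomes, it should keep a correction but name the family, the divisor and the overall alpha before analysis.

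If the data have already been analysed, the report should state the divisor actually used and give unadjusted p-values with the confidence interval. None of this supplies the margin needed before similarity of the two fasting times can be claimed.
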